6.4.1.3 Missing Data

Readers are required to complete evaluating all cases in the two sessions, and missing reader data will be prevented. If any, missing reader data will be reviewed and reported (considered as protocol deviations). No imputation is planned for any study data. The analysis methods would accommodate missing reader data under missing at random assumption.

6.4.2 Statistical Methods for Safety Analyses

No adverse events are anticipated in this study using retrospective cases. Readers are not expected to report any adverse events.

6.4.3 Summary of Baseline Characteristics

The demographic and baseline characteristics of the cases will be assessed by the use of tables

and/or graphs. The baseline characteristic of readers (e.g. confidence on prediction aided tool) will also be assessed in the same way. No statistical tests will be performed on these characteristics.

6.5. Interim Analysis

No interim analysis of study endpoints are planned. The final analysis will be triggered when all the readers complete and record their findings for all the assigned cases at Session 2.

6.6 Multiplicity

The study allocated two-sided $\alpha = 0.05$ to test AUC for 3-year mortality between reading conditions. All the other analyses are exploratory in nature. No multiplicity adjustment will be implemented. The nominal p-value will be reported.

6.7. Sample Size and Power Calculation

This study is well powered for the primary endpoint AUC of 3-year mortality prediction. A sample size of 166 cases and 12 readers was selected for this study. The method of Obuchowski[14] is used to determine the number of readers required in a fully crossed design to provide at least 80% power to detect a 0.05 absolute advantage in AUC for reading, at statistical significance level $\alpha = 0.05$ (two-sided). The disease cases to non-disease cases (for 3-year mortality) will be randomly selected with an approximately 1:1 ratio from the patient dataset pool, which is independent from the dataset used to training the prediction tool. A balanced disease vs non-disease design may not reflect the actual disease prevalence in the real-world setting but enhance statistical efficiency in assessing the accuracy of diagnostic tests. The sample size calculations conservatively assume that both readers and cases are random effects.

Due to this being a pilot study, there were no estimate of variance components. Variance component estimates (via Obuchowski and Rockette approach using jackknife method) from previous MRMC studies that use a similar study design as the proposed (regardless of the original endpoint types) were leveraged in the power and sample size calculation of this study. All power estimates are dependent upon the appropriateness of the assumed variance components.

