4.2. Case Population

The study will target 166 CRLM patients receiving simultaneous resection.

Inclusion Criteria:

- ≥ 18 years old
- confirmation of histologically diagnosed liver metastases of colorectal adenocarcinoma
- receiving colorectal resection with simultaneous liver resection.

Exclusion Criteria:

- presence of other malignancies
- absence of follow-up data
- patients who were followed up postoperatively for less than 5 years and had no occurrences of death.

5. Study Procedure

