5.5. Data Security

All case data used in this study is completely anonymized. This includes any identifying information (e.g. patient name) displayed to readers. All data collected in this reader study will be securely maintained by Cancer Hospital, Chinese Academy of Medical Sciences.

6. Statistical Plan

Study Design Overview	A retrospective, MRMC study, employs a fully crossed design in which all readers (physicians) review medical records from all cases (patients) in two visits separated by a memory washout period of approximately 5 weeks.
Analysis Population	The intention-to-treat (ITT) population will serve as the population for primary efficacy analysis. All randomized participants (readers and cases) will be included in this population.
Primary Endpoints	AUC-ROC
Secondary Endpoints	Sensitivity Specificity Interrater reliability
Statistical Methods	The primary endpoints, between reading conditions, will be compared using the standard MRMC analysis of variance (ANOVA) method of Obuchowski and Rockette (OR)[14], where both reader and case are random effects.
Interim Analyses	No interim analysis of study endpoints is planned.
Multiplicity	Other analyses will be exploratory in nature. No multiplicity adjustment will be implemented. Nominal p-value will be reported.
Sample Size and Power	A sample size of 166 cases (90 experienced OS events within 3 years),

	and 12 readers was selected for this study. The AUC for predicting 3-year mortality is designed for two-sided $\alpha = 0.05$ and power of at least 80% to detect a 0.05 absolute advantage in AUC for reading with an assistant of the CRLM prediction tool.
--	---

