6.2.2 Secondary Endpoints

AUCs: Area Under the Receiver Operating Characteristic Curve (AUC-ROC)

Objective: To evaluate aid versus without aid with respect to (improved) AUC-ROCs for post-operative prediction of post-operative 1-year recurrence, 3-year recurrence, 5-year recurrence, 1-year mortality, and 5-year mortality made by readers.

Sensitivity: the ratio of true positives to total (actual) positives.

Objective: To evaluate aided versus unaided with respect to (improved) sensitivity for prediction of post-operative 1-year, 3-year, and 5-year recurrence and mortality made by readers.

Specificity: the ratio of true negatives to total (actual) negatives.

Objective: To evaluate aided versus unaided with respect to (improved) specificity for prediction of post-operative 1-year, 3-year, and 5-year recurrence and mortality made by readers.

Inter-rater reliability: the consistency of ratings made by readers on the cases

Objective: To evaluate aided versus unaided with respect to (improved) inter-rater reliability for rating on the likelihood of post-operative 1-year, 3-year, and 5-year recurrence and mortality made by readers.

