6.4. Statistical Methods

6.4.1 Statistical Methods for Efficacy Analyses

6.4.1.1 Primary Endpoints

AUC-ROCs for 1-year, 3-year, 5-year of recurrence and mortality will be estimated for each reader in **each review condition** (aided or unaided, and the difference between them) based on the reader's interpretations of all cases. The account for right-censor data, the inverse probability of censoring weighting estimate was used for the cumulative/dynamic time-dependent ROC curve approach by Blanche et al. [15].

AUC-ROCs between reading conditions will be compared using the standard MRMC analysis of variance (ANOVA) method of Obuchowski and Rockette (OR), where both reader and case are random effects, to ensure generalization of the study results to both the population of readers and the population of cases.

The average AUCs within each reading condition, as well as its standard error and two-sided 95% confidence intervals (CIs) will be reported. The average difference in AUCs, its standard error, corresponding two-sided 95% CIs, and statistical inference will be computed, referencing to the approach in Obuchowski and Rockette. No adjustments for covariates are planned.

Sensitivity analysis may be conducted using OR approach with only reader (sensitivity analysis 1) and only case (sensitivity analysis 2) as random effects.

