6.4.1.2 Secondary Endpoints

Analyses of sensitivity and specificity will also use standard MRMC ANOVA methods to compare reader performance under different reading condition and use two-sided 95% CIs to quantify uncertainty. Sensitivity and specificity each provide additional information needed to understand the expected impact of using the prediction tool on clinical practice. Their analysis and reporting, including confidence intervals, is thus required to provide a complete description of reader performance.

Analysis of Inter-rater reliability or other ordinal outcomes collected under different reading condition will use generalized linear mixed model (for appropriate link function) with reading condition as a covariate and both reader and case are random effects.

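### Sampling cases about 1:1 on 3-year death shifts the reported 1-year mortality AUC and specificity levels (and slightly the 5-year AUC) unless the eligible pool already has about 54% three-year deaths; the primary endpoint is unaffected

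*Protocol*

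**What the plan says.** Section 6.7 draws the cases by outcome: "The disease cases to non-disease cases (for 3-year mortality) will be randomly selected with an approximately 1:1 ratio from the patient dataset pool". The Section 6 statistical plan table gives the result: "A sample size of 166 cases (90 experienced OS events within 3 years"), which leaves 76 three-year survivors.

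Section 6.4.1.1 then estimates recurrence and mortality AUCs at 1, 3 and 5 years for each reader on all of these cases. The only weighting it names is for censoring: "the inverse probability of censoring weighting estimate was used for the cumulative/dynamic time-dependent ROC curve approach". It treats readers and cases as random "to ensure generalization of the study results to both the population of readers and the population of cases", and commits to levels as well as contrasts: "The average AUCs within each reading condition, as well as its standard error and two-sided 95% confidence intervals (CIs) will be reported".

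Section 6.2.2 adds sensitivity at each horizon and a comparison "with respect to (improved) specificity for prediction of post-operative 1-year, 3-year, and 5-year recurrence and mortality made by readers". Section 6.4.1.2 says of these two measures: "Their analysis and reporting, including confidence intervals, is thus required to provide a complete description of reader performance".

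Section 4.2 excludes "patients who were followed up postoperatively for less than 5 years and had no occurrences of death". Sections 1.5 and 6.6 make everything except the 3-year mortality AUC exploratory. Section 6.7 accepts that the balanced sample may not match real-world prevalence and gives efficiency as the reason.

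**The concern.** An AUC compares events with non-events, so choosing how many of each to include does not bias it, provided that selection uses the same split as the AUC. That holds at 3 years and not at 1 or 5 years. One-year non-events are a mixture of patients who die in years 1 to 3 and patients alive at 3 years. Five-year deaths are a mixture of deaths before and after year 3. Sampling on 3-year status changes both mixtures.

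The censoring weights cannot repair this. After the Section 4.2 exclusion, vital status at 1, 3 and 5 years is known for every case, so each mortality weight equals 1. The prevalence remark in Section 6.7 does not cover it either: a change of prevalence alone leaves AUC, sensitivity and specificity where they were, whereas here the make-up of the 1-year non-events and the 5-year deaths changes.

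At stake are the reported 1-year mortality levels and their confidence intervals, which a reader could take as describing the eligible patients.

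**Working it through.** **Inputs from the protocol.** 166 cases, 90 three-year deaths (Section 6 table); sampling on 3-year death (6.7); censoring weights only (6.4.1.1); patients alive with under 5 years of follow-up excluded (4.2); risk categories cut at 10, 30 and 70% (3.2). The protocol does not give the share of three-year deaths in the eligible pool, or the cut-off that defines a positive call for sensitivity and specificity.

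**Step 1: sampled share.** 90/166 = 54.2%; 166 - 90 = 76; 90:76 = 1.18:1, consistent with the stated approximate balance.

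**Step 2: what cannot move.** The 3-year mortality events and non-events are the two sampling strata themselves. One-year deaths all lie in the death stratum and 5-year survivors all lie in the survivor stratum. Hence the 3-year mortality AUC, 1-year mortality sensitivity and 5-year mortality specificity are unchanged.

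**Step 3: plausible pool share.** Let m3 and m5 be 3- and 5-year mortality before the follow-up exclusion, and d the fraction of 5-year survivors lost to it. As a simplification, only 5-year survivors are dropped. Then pool share = m3 / (1 - d(1 - m5)). All mortality figures here are assumptions.
- m3 35%, m5 50%: d = 20, 40, 60% gives 0.35/0.90 = 39%, 0.35/0.80 = 44%, 0.35/0.70 = 50%.
- m3 45%, m5 60%: 0.45/0.92 = 49%, 0.45/0.84 = 54%, 0.45/0.76 = 59%.

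The exclusion pushes the share up, towards and possibly past 54%.

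**Step 4: change of mix at d = 40%.**
- 1/3/5-year mortality 10/35/50%. Pool, year 1-3 deaths among 1-year non-events: (0.25/0.80)/(1 - 0.10/0.80) = 0.3125/0.875 = 36%. Sample: 90 × 0.25/0.35 = 64.3, and 64.3/(64.3 + 76) = 46%. Deaths before year 3 among 5-year deaths: pool 0.35/0.50 = 70%. In the sample, one third of the 76 survivors (0.1875/0.5625) die in years 3-5, which is 25.3, and 90/115.3 = 78%.
- 13/45/60%. The same steps give 45% against 46%, and 75% against 75.5%: almost no change, because the pool is already at 54%.

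**Step 5: size of the shift.** Simulated Weibull proportional-hazards populations (shape 1.0 and 1.4, log hazard ratio 0.7 and 1.0 per SD), scores cut at 10/30/70% predicted risk, sample level minus pool level:

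| Pool share of 3-year deaths | 1-year AUC | 3-year AUC | 5-year AUC |
|---|---|---|---|
| 40% | -0.019 to -0.026 | 0.000 | +0.007 to +0.010 |
| 45% | -0.012 to -0.017 | 0.000 | +0.005 to +0.007 |
| 50% | -0.006 to -0.008 | 0.000 | +0.002 to +0.003 |
| 54.2% | 0.000 | 0.000 | 0.000 |
| 60% | +0.009 to +0.012 | 0.000 | -0.003 to -0.004 |

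At a 40% pool, 1-year specificity moves by about -0.03 to -0.05 if the cut-off is 10%, -0.01 to -0.03 at 30%, and close to 0 at 70%.

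**Step 6: the contrast.** In one aided/unaided example (shape 1.2, log hazard ratio 1.0), the 1-year gain is 0.0388 in a 45% pool and 0.0363 in the sample. Over the models tried, the contrast moved by at most 0.006 at a 40% pool and 0.004 at 45%.

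**Step 7: effect of weighting.** Weights of pool share over sample share, p/0.542 for three-year deaths and (1 - p)/0.458 for survivors, return the pool AUC. In repeated samples of 90 + 76 cases with 12 correlated readers, weighting the 1-year mortality AUC did not raise its standard error (ratio 0.97-0.99). At a 45% pool it lowered root mean squared error from 0.034-0.044 to 0.031-0.039. For 5-year mortality the standard error rose 1-5% at pools of 40-45%, and root mean squared error was about neutral.

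**The case against.** The strongest reply is that levels are not the study's question. Every AUC, sensitivity and specificity objective compares aided with unaided reading of the same cases; that contrast barely moves, and all the affected outcomes are exploratory. This stands, and it is why the point is minor.

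The direction is also unknown. The pool share is not given, the shift vanishes at 54% and reverses above it, and the follow-up exclusion raises the share. At 45 to 50% the 1-year shift is well below the sampling error of the estimate. This stands too.

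The generalisation sentence in Section 6.4.1.1 explains why readers and cases are random effects; it is not a claim that sampled levels equal pool levels. That is fair, but the commitment to report levels with confidence intervals remains.

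A weighted supplement might be in an SAP, which was not available. The sampling rule and the estimator are nevertheless fixed in the protocol itself.

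Three stronger readings are tempting and are not supported. A reader might infer that the 1:1 sampling biases the primary test; it does not, because the 3-year AUC conditions on the sampling strata. A reader might infer that the tool's apparent benefit is distorted; the contrast shows no material change. A reader might infer that all 1-year levels will look clearly too poor, as with a pool near 30% (1-year AUC shift -0.029 to -0.040); none of the pool shares worked out above is that low, and nothing in the protocol fixes the sign.

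**Conclusion.** The point holds in a limited form. Unless the eligible pool has about 54% three-year deaths, the 1-year mortality AUC and specificity reported from this sample are not those of the pool, and the named censoring weights do not correct them. For pool shares of about 40 to 60%, the 1-year AUC shift runs from about -0.03 to +0.012, and the 5-year AUC shift is at most about 0.01 with the opposite sign. The specificity shift depends on a cut-off that the protocol does not show. Recurrence levels rest on the same selected cases and can shift as well, by an amount that depends on the model linking recurrence and death.

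The sizes rest on assumed mortality, an assumed loss to the follow-up exclusion, Weibull survival, and readings that track risk within each stratum. The mechanism and the zero shift at 3 years do not depend on these assumptions. Severity is low: a cheap improvement to exploratory reporting.

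**What to change.** - Record how many eligible patients died within 3 years and how many did not, before sampling.
- Report the 1-year mortality AUC and specificity with inverse sampling-fraction weights (pool count divided by sampled count in each stratum), applied in both the estimate and the jackknife variance, beside the unweighted values.
- State that the 5-year mortality and recurrence levels describe the sampled mix. Weighting them is not recommended: for 5-year mortality it trades bias for variance with no clear gain, and for recurrence the shift is model-dependent.
- State that the weighted values describe the pool as filtered by the Section 4.2 follow-up exclusion, not all operated patients.
- Leave the primary analysis unchanged.

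The cost is two counts that the sponsor should hold, a modest amount of extra programming, and two versions of an exploratory result to present. If the pool is already at about 54%, the weights are all close to 1 and the two versions agree.

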6.8. Subgroup Analysis

To determine whether the advantage of a prediction tool in assisting physicians is consistent across various subgroups, the between reading conditions differences in AUCs (with a nominal 95% CI) will be estimated within each category of the following classification variables:

- Reader Subgroups
 - Reader expertise (junior physician, mid-level physician, senior physician)
- Case Subgroups
 - Age at baseline (<60, ≥ 60)
- Primary Tumor site Subgroups

- Primary tumor site (right half-colon, sigmoid colon, and rectum)

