4.1. Reader Characteristics

A reader study with 12 participating physicians (4 Junior Physician, 4 mid-level Physician and 4 Senior Physician) from the Department of Surgical Oncology of the Digestive Tract will be conducted. The standardized training will be provided to all readers how to use medical record system to get patients data, and how to complete the questionnaire.

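### Section 6.8 asks whether the tool's benefit is consistent across subgroups, but the within-category intervals it names do not compare the categories

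*Protocol*

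**What the plan says.** Section 6.8 gives the purpose of the subgroup analysis as "To determine whether the advantage of a prediction tool in assisting physicians is consistent across various subgroups". It then fixes the method: differences in AUC between reading conditions, with nominal 95% intervals, "will be estimated within each category of the following classification variables". The variables are reader expertise (three levels), age (two categories, cut at 60) and primary tumour site (three categories), so the output is 3 + 2 + 3 = 8 separate estimates. The section names no contrast between categories, no interaction, and no rule for judging consistency.

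Section 4.1 gives the composition of the reader panel: "4 Junior Physician, 4 mid-level Physician and 4 Senior Physician".

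Section 6.7 sizes the study for all readers and cases together: "A sample size of 166 cases and 12 readers was selected for this study", to give "at least 80% power to detect a 0.05 absolute advantage in AUC for reading". It takes variance components from other multi-reader studies and gives none of their values. Sections 1.5 and 6.6 confine formal testing to the AUC for 3-year mortality and class everything else as exploratory, without multiplicity adjustment.

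**The concern.** Consistency is a statement about differences between categories. An interval for one category answers whether the gain in that category differs from zero. Two categories can have the same true gain while one interval excludes zero and the other does not, simply because each is estimated from part of the data.

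The risk is clearest for seniority, where each level has a third of the readers. If the junior interval excluded zero and the senior interval did not, this could be taken to mean that the tool helps juniors but not seniors. The display would not support that conclusion, and it contains no estimate against which to check it.

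**Working it through.** **1. Aim against output.** The aim concerns whether gains are equal across categories. The output is a set of gains, each with its own interval. No listed quantity is a difference between two categories' gains. This mismatch needs no arithmetic.

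**2. The plan's own figure.** The stated power of at least 80% cannot be reproduced, because Section 6.7 gives no variance components. It can be inverted. Under a normal approximation, the standard error (SE) of the 12-reader mean difference that gives exactly 80% power for 0.05 at two-sided 0.05 is

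SE12 = 0.05 / (1.960 + 0.842) = 0.0178.

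With the Obuchowski-Rockette (OR) t-test and Hillis degrees of freedom, the required SE is 0.0163 to 0.0179, depending on the correlation assumed below.

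**3. One seniority level.** Let V be the variance of a single reader's AUC difference, and rho the correlation of these differences between readers (the part due to shared cases). The protocol does not give rho, so it is varied as an assumption from 0 to 0.9. For J readers the variance of the mean is (V/J)(1 + (J − 1)rho). Hence V = 12 × SE12² / (1 + 11 rho), and for 4 readers

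SE4 = SE12 × √[3(1 + 3 rho) / (1 + 11 rho)].

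- rho = 0: SE4 = 0.0178 × √3 = 0.0309. Power is Φ(0.05/0.0309 − 1.96) = 37%.
- rho = 0.2: SE4 = 0.0178 × √1.5 = 0.0219. Power is 63%.
- rho = 0.5: SE4 = 0.0178 × √1.154 = 0.0192. Power is 74%.

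The OR test with Hillis degrees of freedom gives 24%, 56% and 73% at the same correlations.

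**4. Mixed patterns when the gain is identical.** Reader-level differences were simulated as 0.05 plus a shared case term plus a reader-specific term, in three groups of 4. Each group received a 95% interval. A trial counts as mixed if some but not all of the three intervals exclude zero. The OR columns treat the case covariance as known.

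| rho | One-level power (OR, 80% overall) | All three exclude 0 | None excludes 0 | Mixed (OR, 80% overall) | Mixed (normal, 80%) | Mixed (OR, 90% overall) |
|---|---|---|---|---|---|---|
| 0 | 24% | 1% | 44% | 54% | 70% | 63% |
| 0.1 | 44% | 13% | 22% | 65% | 60% | 66% |
| 0.2 | 56% | 27% | 17% | 56% | 47% | 51% |
| 0.3 | 64% | 40% | 15% | 45% | 38% | 37% |
| 0.5 | 73% | 58% | 14% | 28% | 25% | 20% |
| 0.7 | 77% | 68% | 15% | 17% | 16% | 11% |
| 0.9 | 79% | 75% | 17% | 8% | 8% | 5% |

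In the OR columns the mixed rate peaks near rho = 0.1, because at rho = 0 many trials have no interval that excludes zero.

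**5. Other readings of inconsistency (OR, 80% overall power).** At least one pair of intervals fails to overlap in at most 1.5% of trials. Some level has a negative point estimate in 0.4% to 11%.

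**6. A direct comparison.** A one-way F test on the 12 reader-level differences (2 and 9 degrees of freedom) falsely signals inconsistency in 5.0% of trials at every rho, because the shared case term cancels between levels.

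**7. Precision of that comparison.** For two levels of 4 readers the SE of the contrast is √[2(1 − rho)V/4] = SE12 × √[6(1 − rho)/(1 + 11 rho)]. With SE12 = 0.0178 and t(0.975, 9 df) = 2.262, the approximate 95% half-widths are:

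- rho = 0: 2.262 × 0.0437 = 0.099
- rho = 0.2: 2.262 × 0.0219 = 0.049
- rho = 0.5: 2.262 × 0.0121 = 0.027
- rho = 0.9: 2.262 × 0.0042 = 0.009

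At correlations up to about 0.2, the half-width is as large as the 0.05 gain the trial is designed to detect, or larger.

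**8. Age and tumour site.** All 12 readers contribute to each of these categories, so the 4-reader argument does not carry over. The protocol gives no case counts by age or site, so nothing can be calculated.

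**The case against.** Four points can fairly be made for the plan.

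First, separate subgroup estimates with nominal intervals are a common exploratory display. The protocol calls itself a pilot and reserves hypothesis testing for the primary endpoint. This stands, and it keeps the point minor. It does not remove the mismatch, because Section 6.8 still claims to determine consistency.

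Second, a statistical analysis plan that is not shown could add the contrast, and its model and interval method are details normally settled there. This also stands in part. But Section 6.8 does not defer the method: it states an aim and names an output that does not serve it.

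Third, a reader might infer that the design would look inconsistent in about half of trials when the benefit is in fact identical. The protocol does not support that as a general statement. It needs a between-reader correlation of about 0 to 0.3, which Section 6.7 does not give, and a rule that consistency fails when an interval includes zero, which Section 6.8 does not state. Under the other readings above, the rate is much lower.

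Fourth, a contrast between levels of 4 readers may be too imprecise to establish consistency. That is true at low correlations, but it is still an estimate of the quantity in question, with its uncertainty visible.

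**Conclusion.** The point holds as a mismatch between aim and method: Section 6.8 sets out to determine consistency and names only within-category intervals, which do not compare categories.

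Its size can be given for seniority only, and as a range: roughly 8% to 65% of trials would show a mixed pattern despite an identical 0.05 gain, with overall power set at 80%. With overall power at 90% the range is 5% to 66%. These figures assume a between-reader correlation from 0.9 down to 0, the same correlation and variance for all readers, and a judgement based on whether each interval excludes zero. None of these assumptions is stated in the protocol, so no single value within the range should be presented as a property of this trial. Nor does the protocol say that a single-category interval including zero would be taken as evidence of inconsistency; it leaves room for that misreading.

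The primary analysis is unaffected.

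**What to change.** Add to Section 6.8: for each subgroup variable, the between-category difference in the aided-minus-unaided AUC gain will be reported with a nominal 95% interval and labelled exploratory, using seniority as a between-reader factor in the Obuchowski-Rockette model and a jackknife over cases for age and tumour site. Consistency will be judged on these differences, not on whether single-category intervals exclude zero. The within-category estimates can stay as description.

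The cost is a little more analysis work, with no additional readers, cases or data. The contrasts will be imprecise, especially for seniority, so the text should also say that a wide interval containing zero is not proof of consistency.
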